14.1 Definitions

Adverse Event (AE)

Any undesirable experience occurring to a subject, whether or not it is considered causally related to the investigational medical device. An AE may be a clinical finding, a clinical laboratory abnormality or a symptomatic complaint which is considered by the Investigator to be outside the normal variation for that parameter.

Adverse Device Effect (ADE)

Any untoward and unintended response to a medical device. This includes any event resulting from insufficiencies or inadequacies in the instructions for use or the deployment of the device and any event that is a result of a user error.

Device Deficiency

Inadequacy of a medical device with respect to its identity, quality, durability, safety or performance (included malfunctions, use errors and inadequate labelling).

Serious Adverse Event (SAE)

A serious adverse event (SAE) could be any event that suggests a significant hazard, contraindication, side effect, or precaution. The seriousness of an AE relates to its clinical significance and its potential impact on health.

An AE will be considered as serious when:

Lead to death

Lead to serious deterioration in the health of the subject, that either results in:

- a. a life-threatening illness or injury, or
- b. a permanent impairment of a body structure or a body function, or
- c. in-patient or prolonged hospitalization, or
- d. medical or surgical intervention to prevent life threatening illness or injury or permanent impairment to a body structure or a body function

Lead to foetal distress, foetal death or a congenital abnormality or birth defect.

Serious Adverse Device Effect (SADE)

Adverse device effect that has resulted in any of the consequences characteristic of a serious adverse event or that might have led to any of these consequences if suitable action had not been taken or intervention had not been made or if circumstances had been less opportune.

Unanticipated Serious Adverse Device Effect (USADE)

Serious adverse device effect that by its nature, incidence, severity or outcome has not been identified in the risk analysis report.

Incident

Any malfunction or deterioration in the characteristics and/or performance of a device, as well as any lack of labelling or instructions for use which, directly or indirectly, may cause or have caused death or serious deterioration in the health of the patient or of a user or of other persons.

14.2 Adverse Event Intensity/Causality

The Investigator, based on his direct observation or on subjects' report, will record the event according to the current version of CTCAE:

Description	Definition
Grade 1 (Mild):	asymptomatic or mild symptoms; clinical or diagnostic observations only; intervention not indicated.
Grade 2 (Moderate):	minimal, local or noninvasive intervention indicated; limiting age-appropriate instrumental daily life activities.
Grade 3 (Severe):	medically significant but not immediately life-threatening; hospitalization or prolongation of hospitalization indicated; disabling; limiting self-care daily life activities.
Grade 4 (Life-threatening consequences):	urgent intervention indicated.
Grade 5:	death related to AE

The relationship of any AE to the product will be classified by the Investigator as follows:

Description	Definition
Certain	The AE is clearly related to the study product
Probable	The AE is likely related to the study product
Possible	The AE may be related to the study product
Doubtful	The AE is unlikely related to the study product
None	The AE is clearly not related to the study product
Unknown	Causality is not assessable, for one reason or another, e.g. because of insufficient evidence, conflicting data or poor documentation

14.3 Adverse Event, Device Deficiency, Adverse Device Effect, reporting

The Investigator will record any AEs, Device Deficiency and ADEs occurring during the study. He/She will also co-operate with the Sponsor in connection with the reporting of any SAE/SADE, Serious Incident to the Competent Authority and to the Independent EC, if applicable.

All AEs regardless of severity occurring between recruitment and completion of the study by a subject must be recorded on the AE form provided with the CRF.

If there is a significant worsening of a medical condition that was present before starting the study, this should be considered as a new AE and a complete evaluation recorded.

Signs and symptoms considered as lack of efficacy and occurring during the study will not be recorded on the AEs Section of the CRF except on the condition that, in the Investigator's opinion, these signs and symptoms are caused by any reason different from lack of efficacy of the study product or meet the definition of serious AE.

In the event of a SADE/SAE, Serious Incident the Investigator has to:

- Complete the relevant CRF pages and a reporting form with the all available initial information,
- Immediately inform the Sponsor or the CRO by telephone,
- Fax the completed report form to the contact person at the Sponsor or the CRO as soon as possible.

SAE/SADE, Serious Incidents reporting contacts are on page 4 of this Clinical Investigation Plan.

The Investigator is responsible for ensuring the follow-up of any subject who experiences an SAE/SADE/ Serious Incident during the study. The investigator must re-examine the subject at regular intervals until the symptoms have completely disappeared or stabilized.

The Sponsor or its delegate will be responsible for reporting the SAE/SADE/Serious Incident to the appropriate Authorities and EC, according to the local regulations.

15. Vulnerable Population

Minors will be recruited for participating in this study. They will receive specifically considered protection in accordance with international and national regulations, GCP guidelines and the provisions of the Declaration of Helsinki.

16. Suspension or Premature Termination of the Clinical Investigation

Unless premature interruption occurs, the end of the study will be the last closure visit at the clinical sites.

16.1 Study Discontinuation

Subjects may be discontinued at any time from the study for any of the following reasons:

- An AE occurs that, in the opinion of the Investigator, makes it unsafe for the subject to continue in the study

- Lack of compliance of the subject to the study treatment or assessments
- The subject needs to use a medication/treatment not allowed
- The subject is lost to follow-up
- The subject dies
- The subject withdraws consent
- The Investigator, for any reason, terminates the entire study, or terminates the study for that subject or the attending physician requests that the subject be withdrawn for any medical reason
- The Sponsor or the Regulatory Authority or the Ethics Committee, for any reason, terminates the entire study or terminates the study for this site or this particular subject.

If a subject is discontinued from the study, the Investigator will, as far as possible, complete the end of study visit (Visit 4) CRF pages. The Investigator should try to ascertain the reason(s) for withdrawal, while fully respecting the subject's rights.

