6.1 General

This is a multicenter, open label, uncontrolled, post-market clinical follow-up investigation.

All the subjects will be allocated to the following treatment group:

- PAPIX ACNE SCAR, topically applied twice a day for 8 weeks.

The subject will start treatment on the first day of study and will go on until 8 weeks after the first administration.

Each subject for whom written consent is obtained will be assigned a five-digit screening code, consisting of the site code (01 or 02) and a progressive number within the site: for example the first subject screened at site 01 will be assigned the code 01-001, the second one 01-002 etc.

All screened subjects will receive the code irrespective of whether or not they will receive the treatment. If a subject discontinues from the study at any time, the code will not be re-used.

All subjects who will sign the informed consent and receive the screening code will be entered into a Subject's Register, containing the name and surname of the patients and their Screening numbers. The Subject's Register will be accessible for source data verification but will be preserved only at clinical site.

Once eligibility of a patient is established (see Inclusion/Exclusion Criteria) the study treatment will be assigned.

The Investigator will keep record of all enrolled patients in the Subject's Screening/Enrolment Log: the subject screening number, the date of consent, the treatment assigned to the patient, if applicable, or the reason for not actively entering the study will be recorded.

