7.1 Sample Size Determination

An exact binomial test with a nominal 5% two-sided significance level will have 80% power to detect the difference between the Null hypothesis proportion, π_0 of 0.5 (i.e., 50% of patients with treatment success) and the Alternative proportion, π_1 , of 0.75 (i.e., 75% of patients with treatment success) when the sample size is 30 subjects. Assuming a possible 25% dropout rate, 40 subjects will be enrolled.

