7.3.1 Missing Data

Missing data will not be replaced in any statistical analysis.

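### Section 16.1 allows withdrawal from the whole study on wide discretion, and no Week 4 assessment is sought once a subject stops the product

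*Protocol*

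**What the plan says.** Protocol 16.1 opens with "Subjects may be discontinued at any time from the study for any of the following reasons". The list that follows includes:

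- "Lack of compliance of the subject to the study treatment or assessments";
- "The subject needs to use a medication/treatment not allowed";
- "The Investigator, for any reason, terminates the entire study, or terminates the study for that subject";
- for the sponsor, regulatory authority or ethics committee, a power that "for any reason, terminates the entire study or terminates the study for this site or this particular subject".

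There is no category for a subject who stops the gel but stays under observation. For a discontinued subject, 16.1 asks that the Visit 4 CRF pages be completed as far as possible and that the investigator try to find out the reason. Protocol Table 1 marks Visit 4 as doubling as the early-termination visit, with SGA and the scar and lesion counts ticked.

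The primary endpoint is fixed at Week 4, Visit 3, Day 28 ± 3 (Protocol synopsis and Table 1; SAP 5.1). Protocol 7.3.1 states "Missing data will not be replaced in any statistical analysis", and SAP 9.1.4 repeats it. FAS membership needs only one post-baseline assessment of any performance endpoint (Protocol 7.2; SAP 8.1). On design, Protocol 6.1 says "This is a multicenter, open label, uncontrolled, post-market clinical follow-up investigation". On losses, Protocol 7.1 says "Assuming a possible 25% dropout rate, 40 subjects will be enrolled".

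**The concern.** A subject withdrawn from the study at, say, Day 14 may be perfectly willing to return on Day 28, yet nothing in the plan asks for that visit. The assessment at leaving is not a Week 4 result. It is entered on Visit 4 pages, and no rule ties it to Visit 3. With no replacement of missing data, the subject can sit in the FAS through an early assessment and still contribute nothing to the primary proportion.

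The reason for leaving matters because the discretion is wide. The study is open label, the skin is assessed at every visit, and no blinded or independent reading of the SGA, the scar count or the photographs is described. Whoever decides on a discontinuation can therefore know how the scars are responding. Section 16.1 gives no threshold for non-compliance; the 20% limit on skipped applications appears only in SAP 9.1.3, as a definition of compliance.

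The primary test compares one proportion with a fixed 50%, so there is no control arm in which the same selection would occur. If withdrawals before Week 4 are mainly failures, the observed proportion rises directly.

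**Working it through.** **Inputs.** Exact binomial test, two-sided 5%, null 0.50, alternative 0.75, 30 evaluable subjects, 25% dropout, 40 enrolled (Protocol 7.1; SAP 7). The number of withdrawals before Visit 3, and their outcomes, are not in the documents and are assumed below.

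**1. The plan's own figure.** Let c(n) be the smallest count with P(Bin(n, 0.5) ≥ c) ≤ 0.025. For n = 30, P(X ≥ 20) = 0.0494 and P(X ≥ 21) = 0.0214, so c(30) = 21. Power is P(Bin(30, 0.75) ≥ 21) = 0.803. Enrolment is 30 / (1 − 0.25) = 40. Both stated figures reproduce.

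**2. Worst-case effect of selective withdrawal.** Suppose 40 subjects, a true success rate of 0.50, and k subjects who would have failed withdrawn before Week 4 and omitted. The test then uses n = 40 − k, while the number of successes is still Bin(40, 0.5). The upper-tail false-positive rate is P(Bin(40, 0.5) ≥ c(40 − k)), and the expected observed proportion is 20 / (40 − k).

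| Failures removed, k | n analysed | c(n) | Expected proportion | Upper-tail false-positive rate |
|---|---|---|---|---|
| 0 | 40 | 27 | 50.0% | 1.9% |
| 1 | 39 | 27 | 51.3% | 1.9% |
| 2 | 38 | 26 | 52.6% | 4.0% |
| 4 | 36 | 25 | 55.6% | 7.7% |
| 5 | 35 | 24 | 57.1% | 13.4% |
| 10 | 30 | 21 | 66.7% | 43.7% |

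The nominal upper tail is 2.5%. One removed failure changes nothing and two already exceed that level. Ten is the whole dropout allowance (0.25 × 40), with every loss a failure and every loss before Week 4.

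**3. How much can hinge on unseen Week 4 results.** With 40 enrolled and 30 observed, 21/30 = 70% gives two-sided p = 0.043. The same 21 successes with the ten unseen subjects counted as failures is 21/40 = 52.5%, p = 0.87.

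**The case against.** Much can be said for the plan, and several stronger readings fail.

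- **A reader might infer that the outcome is never collected.** The documents do not support that. SGA and scar count are foreseen at the early-termination visit, as far as possible. What is missing is an assessment at Week 4 and a rule relating the early one to the endpoint.
- **A reader might infer that 16.1 compels removal.** It says that subjects may be discontinued. That stands, although permission without criteria is itself the discretion at issue.
- **A reader might infer that any adverse event leads to withdrawal.** The listed reason requires an event that makes it unsafe, in the investigator's opinion, to continue.
- **A reader might infer that the FAS and the per-protocol set will largely coincide.** The per-protocol definition excludes users of forbidden medication, so the plan expects some of them in the FAS. SAP 9.1.3 classifies non-compliers and SAP 11.5 summarises adherence in the FAS, which also implies that they can remain.
- **Only withdrawals before Visit 3 touch the primary endpoint.** This stands; later losses leave it intact.
- **The inflation arises because missing results are omitted, and counting them as failures would remove it.** This is true, but no analysis rule recovers an unmeasured outcome, and that rule is costly. With 75% success among those observed, 10% missing gives a rate of 0.75 × 0.90 = 0.675 and power of 57.4% at n = 40. With 25% missing, the rate is 0.5625 and power 10.0%.
- **Day 28 results obtained after a prohibited treatment could credit that treatment's effect to the gel.** This is a sound objection to unqualified follow-up, and the fix has to meet it.
- **Reasons for withdrawal are already reported** (SAP 10.1, Listing 16.2.1). They are, but who decided is not required.

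**Conclusion.** The point holds in a limited form. Section 16.1 permits withdrawal from the study on broad grounds in an open-label single-arm trial, no Week 4 assessment is sought after the product is stopped, and the use of an early-termination assessment is undefined. A subject withdrawn before Day 28 therefore has no primary result even if one was obtainable.

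The direction of any bias is upward if those subjects are mainly failures. The size runs from nil (one failure removed) to a false-positive rate of 43.7% (ten). These are upper bounds: they assume a true rate of 50% and that every removed subject would have failed. The documents show neither how many withdrawals would occur before Visit 3 nor whether they would depend on outcome, so bias is possible but not demonstrated.

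A reader might also infer that keeping these outcomes would add power. That should not be claimed. It assumes the retained subjects succeed at 75%, the opposite of the assumption behind the bias figures. Even then the exact test is discrete: power at 75% is 80.3% with 30 subjects, 77.1% with 31 and 73.7% with 32.

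**What to change.** Leave the reasons for stopping the product unchanged, and divide 16.1 into stopping the product and leaving the study.

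1. Unless consent is withdrawn, or the subject dies or is lost to follow-up, ask a subject who stops the product to attend Visit 3 (Day 28 ± 3) and Visit 4 for the scheduled SGA, scar and lesion counts, IGA and photographs.
2. Analyse these results in the FAS at the visit they belong to. Flag any obtained after a prohibited treatment, and show the primary result also with those subjects counted as non-successes, so that improvement from another treatment is not credited to the device.
3. State that an early-termination assessment made before the Day 28 window is not used as the Week 4 result.
4. Record who decided each discontinuation, the reason and the date, and show them in Listing 16.2.1.

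The cost is protocol and SAP wording plus one extra summary, using visits already scheduled. The downside is that the FAS will include some off-product outcomes, and the success rate may shift slightly.

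SAP 7 describes the 40 subjects as already enrolled, so new wording may come too late for this cohort. If collection can no longer change, list for each discontinuation before Visit 3 the decider, reason, date, and last SGA and scar count, so that readers can judge whether the omitted subjects were failing.

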Population	
The following populations are defined for this investigation:
 
•Safety analysis set (SAF): all patients enrolled who sign informed consent and receive at least one administration of the investigational device.•Full analysis set (FAS): all patients of the SAF who have performed the baseline assessments and have at least one post-baseline assessment of any performance endpoint.•Per-Protocol analysis set (PPAS): all patients of the FAS who meet all inclusion/exclusion criteria and who do not have any major protocol deviation. 
The analysis of safety endpoints will be performed in the Safety population (SAF). Analysis of performance endpoints will be performed on the FAS population. The analysis of primary endpoint will be repeated in the PPAS.

------------	--

Table 1: Study Flow-Chart

	Visit 1	Visit 2	Visit 3	Visit 4*
	Week 0	Week 2	Week 4	Week 8
	Day 1	Day 14 ± 3	Day 28 ± 3	Day 56 ± 3
	Screening Baseline Treatment start	Follow-up visit	Follow-up visit	End of treatment End of study
Written informed consent	✓			
Demographic data	✓			
Medical and surgical history	✓			
Physical examination (only dermatologic)	✓			✓
Inclusion and exclusion criteria	✓			
Acne scars and lesions count	✓	✓	✓	✓
Scars Global Assessment (SGA)	✓	✓	✓	✓
Acne Investigator Global Assessment (IGA)	✓	✓	✓	✓
Face photos	✓	✓	✓	✓
Skin evaluation (roughness, texture)	✓	✓	✓	✓
Study product dispensed	✓		✓	
Study product administration	→ (twice daily)			
Study product returned			✓	✓
Global evaluation of performance ¹				✓
Global evaluation of product acceptability ²				✓
Treatment compliance		✓	✓	✓
Concomitant medications/treatments	✓	✓	✓	✓
Local and general adverse events		✓	✓	✓

*Or Early termination Visit

¹To be evaluated by both the subject and the Investigator

²To be evaluated by the subject

2. Identification and Description of the Investigational Device

PAPIX ACNE SCAR is a silicone gel for acne lesions and scars. It is indicated to treat oily, blemished or acneic skin.

With regular use, PAPIX ACNE SCAR helps to improve acne skin and visibly improves the appearance of acne scars, while moisturising the skin. Thanks to its formulation, the medical device helps:

- improving acneic skin within 30 days;
- improving visible acne scars & marks;
- preventing the development of new acne lesions and scars.

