6.4 Procedures

6.4.1 Study Visits and Assessments

Visit 1 screening – baseline- treatment start (day 1):

Subjects will be evaluated with regard to the inclusion and exclusion criteria that will allow their participation into the study.

Before any study specific evaluation is carried out, subjects will receive all the information about the study by the Investigators and will sign an informed consent form. In the case of minors, the informed consent form shall be signed by the parents or the guardian.

The following activities will be performed:

- Collection of information about demography
- Medical and surgical history
- Acne medical history (duration, previous treatments)
- Physical examination (only dermatologic)
- Face cutaneous examination:
 - type of skin (dry/normal/oily)
 - site of acne lesions (on the face) and count
 - acne scars count
 - acne scars global assessment by the SGA
 - acne global assessment by IGA
 - roughness and skin texture evaluations
- Photographs of the face
- Previous (in the 6 months before) and concomitant medications/treatments recording
- Inclusion/exclusion criteria assessment
- Study product delivery to subject and instructions on how to use it
- Recommendations for face cleaning to follow.

Recommendations for face cleaning to follow: throughout the study subjects will be required to avoid soap and use only the product Papix cleanser for their face. The product will be provided by the Sponsor of the study. No other cleanser other than the product provided by the Investigator will be permitted.

PAPIX ACNE SCAR application: apply twice a day for 8 weeks, 2 FTU (finger tip units) in the morning and in 2 FTU the evening before bedtime, on the face, and massaged gently into the skin until absorbed.

Visits 2 and 3 – follow-up (Day 14 ± 3 and 28 ± 3, respectively):

The following activities will be done at visit 2 and 3:

- Face cutaneous examination:
 - acne scars and lesions count
 - acne scars global assessment by the SGA
 - acne global assessment by IGA
 - roughness and skin texture evaluations
- Photographs of the face
- Changes in concomitant medications/treatments recording
- Study product collection and new delivery to subject (only at visit 3)
- Treatment adherence check with the subject
- Recommendations for face cleaning to follow
- Adverse events (occurred since previous visit) recording.

Visit 4 – End of treatment and end of study (Day 56 ±3):

The following activities will be done at visit 4:

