5. STUDY ENDPOINTS

5.1 Primary Endpoints

Proportion of subjects with improved acne scars and marks at week 4 of treatment (Visit 3) and, at the same time, without any new facial acne scars with respect to baseline (Visit 1).

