5.2 Secondary Endpoints

Secondary endpoints were:

- 1. Proportion of subjects with improved acne scars and marks at week 2 and 8 of treatment (Visits 2 and 4) and, at the same time, without any new facial acne scars with respect to baseline (Visit 1).
- 2. Proportion of subjects at week 2, 4 and 8 of treatment, without any new facial acne lesions with respect to baseline (Visit 1).
- 3. Change from baseline (Visit 1) to each following time point in the acne severity, according to the Investigator Global Assessment.
- 4. Change from baseline (Visit 1) to each following time point in the skin roughness, on a 4-point scale from 0 (none; very smooth) to 3 (severe; very rough).
- 5. Change from baseline (Visit 1) to each following time point in the skin texture on a 6-point scale from 0 (worse) to 5 (complete improvement).
- 6. The subject's adherence to treatment by the product accountability.
- 7. The subject's and Investigator's global evaluation of satisfaction with regards to the performance of PAPIX ACNE SCAR, through a specific questionnaire.
- 8. To evaluate the subject's overall acceptability of the treatment, through a specific questionnaire.

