9.1.4 Methods for Withdrawals and Missing Data

Missing data will not be replaced in any statistical analysis.

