11.5 Summary of Efficacy Analyses

Endpoint	Analysis	Populations
Proportion of subjects with improved acne scars and marks at week 4 of treatment (Visit 3) and, at the same time, without any new facial acne scars with respect to baseline (Visit 1).	Exact binomial test	FAS PP
Proportion of subjects with improved acne scars and marks at week 2 and 8 of treatment (Visits 2 and 4) and, at the same time, without any new facial acne scars with respect to baseline (Visit 1).	Exact binomial test	FAS
Proportion of subjects at week 2, 4 and 8 of treatment, without any new facial acne lesions with respect to baseline (Visit 1).	Exact binomial test	FAS
Change from baseline (Visit 1) to each time point (Visit 2, 3 and 4) in the acne severity, according to the Investigator Global Assessment.	Wilcoxon signed rank- sum test	FAS
Change from baseline (Visit 1) to each time point (Visit 2, 3 and 4) in the skin roughness, on a 4-point scale from 0 (none; very smooth) to 3 (severe; very rough).	Wilcoxon signed rank- sum test	FAS
Change from baseline (Visit 1) to each time point (Visit 2, 3 and 4) in the skin texture on a 6-point scale from 0 (worse) to 5 (complete improvement).	Number (N) and the proportion of subjects (%) for each item	FAS
Subject's and Investigator's global evaluation on performance of the study product at the end of the study (Visit 4) by means of a 7-items scale.	Number (N) and the proportion of subjects (%) for each item	FAS
Subject's overall acceptability of the treatment at the end of the study (Visit 4) by means of a 5-item scale.	Number (N) and the proportion of subjects (%) for each item	FAS

Subject's adherence to treatment by the product accountability.	Mean percentage within each treatment group	FAS
---	---	-----

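### Early-termination assessments share the Visit 4 label with Week 8, and the SAP has no rule that assigns them by study day

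*Protocol*

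**What the plan says.** **Where the data are recorded.** Protocol 16.1 states that for a discontinued subject "the Investigator will, as far as possible, complete the end of study visit (Visit 4) CRF pages". In the study flow-chart (protocol Table 1), the column headed Visit 4, Week 8, Day 56 ± 3 carries the footnote "Or Early termination Visit". One visit label therefore covers two different times.

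**Scheduled times.** Protocol 6.4.1 gives "Visits 2 and 3 – follow-up (Day 14 ± 3 and 28 ± 3, respectively" and "Visit 4 – End of treatment and end of study (Day 56 ±3", each in days.

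**How the SAP reads the labels.**
- SAP 5.1 defines the primary endpoint as "Proportion of subjects with improved acne scars and marks at week 4 of treatment (Visit 3", so Week 4 is Visit 3.
- SAP 5.2 has "Proportion of subjects with improved acne scars and marks at week 2 and 8 of treatment (Visits 2 and 4", so Week 8 is Visit 4.
- The table in SAP 11.5 does the same for the scales, for example "Change from baseline (Visit 1) to each time point (Visit 2, 3 and 4) in the acne severity".

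**What is tested at Week 8.** Under SAP 11.4.2 the scar composite and the no-new-lesions proportion are tested against 50% with the exact binomial test. IGA and roughness changes are tested with the Wilcoxon signed-rank test. Texture is tabulated.

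**Who is included.** The FAS (SAP 8.1) needs only one post-baseline assessment of any performance endpoint, so early stoppers stay in it.

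**The rule on withdrawals.** SAP 9.1.4, whose heading covers withdrawals and missing data, says only "Missing data will not be replaced in any statistical analysis". The variable list in SAP 9.1 has no study day or analysis visit, and the mock efficacy tables have no row for early termination.

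**The concern.** Week 8 results are meant to describe eight weeks of treatment. If the tables are built from the visit label, they mix eight-week outcomes with outcomes from any earlier day. The earlier outcomes come from subjects selected for stopping: the reasons in protocol 16.1 include adverse events, non-compliance and need for a treatment that is not allowed. In effect an earlier value would stand in for a missing Week 8 value, which is what SAP 9.1.4 says will not be done.

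The primary endpoint has a narrower exposure. A subject who stops inside the Visit 3 window may be assessed on time for Week 4 and yet have that assessment stored only as Visit 4. Neither document says how to treat either case, so the choice would fall to the analyst of an open-label study.

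**Working it through.** **1. The plan's own figure.** Inputs from protocol 7.1 and SAP 7: null 0.50, alternative 0.75, two-sided 5%, 30 evaluable, 25% dropout, 40 enrolled.

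For s successes in n with s > n/2, the exact two-sided p-value against 0.5 is 2 × Σ C(n,k) × 0.5ⁿ, summed over k = s to n.
- The smallest significant count at n = 30 is 21, with p = 0.0428.
- Power at 0.75 is P(X ≥ 21) = 0.803.
- Inflation is 30 / (1 − 0.25) = 40.

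The stated 80%, 30 and 40 reproduce and are not in dispute.

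**2. Windows in days.** Visit 2 is 14 ± 3 = Days 11-17. Visit 3 is 28 ± 3 = Days 25-31. Visit 4 is 56 ± 3 = Days 53-59. A stop on Day 18 lies in no window, yet its assessment carries the Visit 4 label. A stop on Day 26 lies in the Visit 3 window, but 16.1 directs its data to the Visit 4 pages.

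**3. Ceiling.** 0.25 × 40 = 10 early-termination records. This needs every planned dropout to occur and to be assessed on stopping.

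**4. Week 8 test.** All success counts are assumed.

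| Completers | p | Early stoppers added | Pooled as Visit 4 | p |
|---|---|---|---|---|
| 22/30 | 0.016 | 3/10 | 25/40 | 0.154 |
| 22/30 | 0.016 | 0/10 | 22/40 | 0.636 |
| 21/30 | 0.043 | 0/10 | 21/40 | 0.875 |
| 21/30 | 0.043 | 5/10 | 26/40 | 0.081 |
| 21/30 | 0.043 | 8/10 | 29/40 | 0.006 |
| 20/30 | 0.099 | 8/10 | 28/40 | 0.017 |

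The result can cross 0.05 in either direction.

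**5. Fewer early stoppers.** Suppose 30 completers succeed at 75% and k early stoppers at 25%. The expected pooled proportion is (30 × 0.75 + k × 0.25) / (30 + k):
- k = 2: 23.0/32 = 71.9%
- k = 4: 23.5/34 = 69.1%
- k = 10: 25.0/40 = 62.5%

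**6. Primary endpoint, one record moved.** Start from 21/30 (p = 0.043), the smallest significant result.
- One on-time success stored as Visit 4 and dropped: 20/29, p = 0.061.
- The same subject kept in the denominator as a non-success: 20/30, p = 0.099.
- One on-time failure stored as Visit 4 and dropped: 21/29, p = 0.024.

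The SAP does not say whether an FAS subject without a Visit 3 value is dropped or counted as a non-success.

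**The case against.** A reader might infer more than the documents support, in four ways.

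- **That the SAP puts early stoppers into Week 8.** It never says so. SAP 11.4.2 also describes the scar, IGA and texture time points by weeks on treatment, and an assessment on Day 18 is not an eight-week outcome. An analyst could exclude it by date. What stands is that visit label and elapsed time disagree for these subjects, and nothing says which governs.
- **That the primary analysis routinely loses on-time assessments.** This needs a stop in Days 25-31 and blank Visit 3 pages. Protocol 16.1 does not say that the Visit 4 pages replace the Visit 3 pages due that week. If both are completed, the Week 4 value survives.
- **That 10 of 40 Week 8 values are affected.** The 25% is a planning allowance. Loss to follow-up, death and withdrawn consent often yield no final assessment, and 16.1 asks only for best effort.
- **That the global evaluations are contaminated too.** SAP 11.5 defines performance and acceptability at end of study (Visit 4), not at Week 8. An evaluation given on stopping fits that definition.

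There are also partial safeguards: disposition by visit with reasons for withdrawal (SAP 10.1), deviation review before database lock (SAP 10.2), and listings of discontinued and excluded subjects (16.2.1 and 16.2.3). They make early stops visible but do not say where the data belong.

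**Conclusion.** The concern holds as a gap in the analysis rules that has a definite consequence if visit labels are followed. Early-termination outcomes would count as Week 8 outcomes for the scar composite, new lesions, IGA, roughness and texture, in conflict with the eight-week wording and with SAP 9.1.4. In the narrower case of a stop in Days 25-31 recorded only on the Visit 4 pages, the primary endpoint would have no Visit 3 value.

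The documents do not give the number affected. Ten of 40 is a ceiling, and every success count above is an illustration. Within that range the Week 8 exact test can move across 0.05 either way, and a borderline primary result can turn on one record. The main effect is on secondary results, for which SAP 9.3 makes no multiplicity adjustment. The SAP should be corrected; the design and the sample size are not called into question.

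**What to change.** Add to SAP 9.1, before database lock, a rule for early-termination assessments only:

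1. An early-termination assessment inside a scheduled window (Day 14 ± 3, 28 ± 3 or 56 ± 3) counts as that visit if no scheduled assessment exists for it. One in Days 25-31 then enters the primary analysis as Visit 3.
2. An early-termination assessment outside every window is listed as early termination and is not analysed as Week 8.
3. Scheduled visits of continuing subjects keep their nominal label even if slightly out of window. Applying the ± 3-day limits to everyone could remove valid data, such as a Visit 3 held on Day 33.
4. Report the number of FAS subjects without a Week 8 value, and add a sensitivity analysis that counts them as non-successes for the binary Week 8 endpoints.
5. Leave the global evaluations at end of study (Visit 4) as defined.

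**Cost.** One SAP paragraph, one derived analysis-visit variable and one extra analysis, with no new data. This assumes that assessment dates are in the CRF, which is not among the documents; the questionnaires in protocol Appendices 2-4 do carry a completion date.

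**Downside.** Week 8 becomes an observed-case analysis, with smaller denominators and possible selection toward completers. Item 4 shows how much that matters: with 22 successes among 30 observed and 10 subjects absent, the main result is 22/30 (p = 0.016) and the sensitivity result is 22/40 (p = 0.64).
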